## 1.0 TRIAL SUMMARY

Abbreviated Title	PAVE Therapy for Post-RT ED
Trial Phase	Phase II
Clinical Indication	Treatment of radiation-induced erectile dysfunction
Trial Type	Treatment
Type of control	Comparison to baseline in each patient
Route of administration	oral
Trial Blinding	NA
Treatment Groups	Three subgroups will be enrolled, patients who are not on any statins at the time of enrollment, those on atorvastatin, and those on other statins.
Number of trial subjects	50
Estimated duration of trial	4 years
Duration of Participation	1 year

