Statins have been studied for a role in the treatment of established ED, although, until recently, not in the setting of radiation induced ED. A recent meta-analysis of all trials investigating the efficacy of Statin use on non-radiation induced ED showed a clinically and statistically significant increase of 3.4 points on the IIEF. Of note, this was roughly 1/3 to ½ of the effect seen with PDE inhibitors. The most commonly used statins were atorvastatin followed by simvastatin. Statins improve endothelial function both by lowering LDL (low density lipoprotein) levels and by increasing the availability of NO. Thus, statins appear to counteract one of the primary molecular processes implicated in the development of radiation induced ED. A recent secondary analysis of a trial studying the ability of lovastatin to prevent radiation induced rectal injury demonstrated that this agent was effective in preserving erectile function across most domains of the IIEF with a minimum of 2 years follow-up. More potent statins, such as atorvastatin, might prove even more effective in this setting.

As noted above, along with decrease in NO production resulting from the inflammatory response to RT, fibrosis also appears to be a component of radiation induced ED. As such, the combination of Vitamin E and Pentoxifylline may provide a benefit as this combination has a proven role in the treatment of established soft tissue fibrosis from radiation. These drugs have been used for radiation induced proctitis as well as cystitis. Additionally, a recent study has shown that prophylactic Vit E and Pentoxifylline reduces the rate of post-mastectomy fibrosis and implant loss in women with breast cancer. Thus, the addition of Vitamin E plus Pentoxifylline to atorvastatin, as proposed in this study, will target both the proinflammatory and profibrotic pathways known to play a role in late radiation injury.

Another rationale for the combination of these agents is their well-established favorable side effect profile. All of these agents have been used for many years in the clinic and are generally well-tolerated. In addition, are all off-patent and are less costly than the 5-PDE inhibitors.

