**Subject Exclusion Criteria:**

1. No androgen deprivation therapy within the past 12 months
2. No contraindication to an HMG-coA-reductase inhibitor, Vitamin E or Pentoxifylline
3. Not currently taking cyclosporine, the HIV protease inhibitors, hepatitis C protease inhibitors, Gemfibrozil, other fibrates, Clarithromycin, itraconazole or strong inhibitors of CYP3A4
4. No recent cerebral or retinal hemorrhage that in the opinion of the treating physician would make PAVE unsafe (within 6 months)
5. No current chemotherapy during study participation
6. No active liver or muscle disease that in the opinion of the treating physician would make PAVE unsafe.
7. No prior radical prostatectomy, cystoprostatectomy, abdominoperineal resection or retroperitoneal lymph node dissection

8. Not currently taking a 5PDE inhibitor nor have used one within 30 days of enrolling in the study
9. No recent deep venous thrombosis, myocardial infarction or pulmonary embolism (within 6 months) requiring continued anticoagulation other than ASA.
10. No cardiac arrhythmias or artificial heart valves requiring anticoagulation other than ASA.
11. No concurrent drugs with anti-platelet properties (e.g., P2Y12 inhibitors, non-steroidal anti-inflammatory agents, selective serotonin reuptake inhibitors) other than low dose ASA (81mg/d).
12. Not currently taking high dose statin therapy, defined as Rosuvastatin >10mg/d or Atorvastatin >40mg/d.
13. Not currently taking theophylline
14. No history of active peptic ulcer disease in the past 6 months.
15. no history of intolerance to pentoxifylline or methylxanthines such as caffeine, theophylline and theobromine that in the opinion of the treating physician would make PAVE unsafe.
16. No concurrent use of CYP1A2 inhibitors (e.g., ciprofloxacin), ketorolac, or vitamin K antagonists (e.g. warfarin).

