## **5.0 Pre-treatment evaluation**

(must be completed within 8 weeks prior to the completion of second step enrollment in CORe; In the event that a patient cannot be seen in person to consent and is consented remotely, physical exam and vitals are not required prior to enrollment. KPS/ECOG maybe conducted from the telephone calls. Baseline labs could be drawn at outside facility and IIEF-5 questionnaire can be completed at home and both can be submitted via secure email or fax.)

A. History and Physical, including KPS or ECOG. Include the following information at a minimum:

1. Age
2. Race and ethnicity
3. T-stage, N-stage, M-stage, Gleason score, initial PSA, PSA prior to radiation
4. Radiation therapy details:

- a. treatment dates
- b. modality: protons, photons, brachytherapy (include isotope used and dose), or any combination of these modalities
- c. for external beam (photon, proton, or combination):
  - 1. include whether or not pelvic lymph nodes were treated, and if so, report total and daily dose/fraction
  - 2. report total dose and dose per fraction for treatment to prostate +/- seminal vesicles
- 5. Most recent androgen deprivation therapy: report dates of treatment and drugs used
- 6. smoking history
- 7. alcohol history
- 8. current medications including non-prescription substances will be recorded in the medical chart.
- 9. Most recent treatment tried for ED
- 10. complete past medical history including history or presence of diabetes mellitus, hypertension, hyperlipidemias, endocrinopathies, cardiovascular diseases (e.g., coronary artery disease, CVA, TIA), hematologic diseases and psychiatric conditions will be recorded in the medical chart.
- 11. history of prior abdominal &/or pelvic surgery
- 12. current relationship status (i.e., married, widowed, divorced, presence of significant other)

B. Baseline assessment of erectile function using IIEF-5.

C. Laboratory studies: serum testosterone, CK, liver panel, BUN, Creatinine, GFR estimation, CBC, INR, PT, PTT

D. Baseline CTCAE V4.03 items grade 2 or higher: blurry vision, abdominal distension, abdominal pain, bloating, diarrhea, dyspepsia, flatulence, gastrointestinal pain, nausea, vomiting, malaise, pharyngitis, urinary tract infection, bruising, arthralgias, bone pain, generalized muscle weakness, myalgia, headache, rash (maculopapular), flushing

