**Table 1: Patient assessment schedule**

Test	Baseline *** (within 8 wks of enrollment)	6 wk* ± 2 wks	3 mo* ± 2 wks	6 mo* ± 2 wks	9 mo* ± 2 wks	12 mo* ± 2 wks	18 mo ± 4 wks*
H&P	X			X		X	X
BP, Pulse, Respiratory Rate	X	X	X	X	X	X	
KPS or ECOG	X			X		X	
IIEF-5****	X		X	X	X	X	
CTCAE V4.03**	X	X	X	X	X	X	
Hepatic panel	X	X	X	X	X	X	
CK 	X	X	X	X	X	X	
BUN, Creatinine, calculated GFR, CBC, PT, PTT, INR, Testosterone	X	X	X	X	X	X	

In addition to scheduled testing, obtain at any time patient notes muscular symptoms

\*follow up times start from the day patient begins taking all 3 drugs concurrently. Can be done over the phone or in person, in the event that follow up can only be done over the phone, physical exam, KPS or ECOG, and vitals do not have to be obtained. Labs could be drawn at outside facility and IIEF-5 questionnarire can be completed at home and both can be submitted via secure email or fax.

\*\*selected items with CTCAE grade 2 or higher: blurry vision, abdominal distension, abdominal pain, bloating, diarrhea, dyspepsia, flatulence, gastrointestinal pain, nausea, vomiting, malaise, pharyngitis, urinary tract infection, bruising, bleeding, arthralgias, bone pain, generalized muscle weakness, myalgia, headache, rash (maculopapular), flushing, chest pain, palpitations, dyspnea, cough, wheezing, lower extremity edema. This assessment can be done either over the phone or in person.

\*\*\*please refer to section 5.0 for pre-treatment evaluation

\*\*\*\*please refer to the appendix for the IIEF-5 questionnaire

D. **Modification of statin dosing**

1. discontinue if transamimases become  $\geq$  3 times ULN
2. discontinue if creatine kinase becomes  $\geq$  5 times ULN
3. If not on a statin prior to enrollment in the trial, discontinue if signs or suspicion of cardiovascular issues appear per the discretion of the treating physician.

For other side effects listed in section 8 above:

- a. if dose is  $\geq$ 20mg and if toxicity is Grade 2, decrease dosage by 50%. If toxicity resolves or decrease to Grade 1, maintain atorvastatin at this lower dose. If toxicities are  $\geq$ Grade 3, stop atorvastatin and the patient should be removed from the study.
- b. If dose=10mg, hold atorvastatin. If toxicity resolves or decrease to Grade 1, restart at 10 mg every other day. If toxicities are  $\geq$ Grade 3, stop atorvastatin and the patient should be removed from the study.

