## **B. Endpoints**

### **i. IIEF-5 (International Index of Erectile Function)**

This validated instrument will be completed as per study calendar. The instrument categorizes ED severity into 5 categories as none (22-25), mild (17-21), mild to moderate (12-16), moderate (8-11), or severe (5-7). A patient will demonstrate improvement at any time point if his score goes up enough to move at least 1 category less severe compared to baseline. A patient with improvement will be considered to have a response. Patients who drop out of the trial without any measurements will count as a non-responder.

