**C. Sample Size**

A total of 50 patients will be enrolled. With 50 patients, if the response rate is 33%, then assuming an uninformative prior of beta(0.33, 0.67), the 95% credible interval would be (20.1%, 45.3%) if 16/50 respond and (21.8%, 47.4%) if 17/50 patients respond. The selection of 50 patients provides a 95% credible interval that has a width less than 26% at approximately 33%.

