**D. Interim Analyses for Safety and Futility**

Interim analyses will begin after 10 patients have been enrolled. Monitoring will then be performed every 10 patients to ensure that patients are exhibiting reasonable toxicity and efficacy rates to continue with the trial. Patients who receive treatment less than 8 weeks will still be counted in toxicity and futility monitoring as long as they received at least 1 dose of the study drug. For patients already on statins, this means the patient must have started the combination. For patients who are starting on atorvastatin, patients will count as long as they received at least one dose of atorvastatin. If the trial can continue after 40 patients, then interim analyses will be complete. Adverse events will continue to be recorded and reported for all patients. If the toxicity or efficacy rates are noted to be different among the patient subgroups, the same stopping rules may be applied to any subgroup of concern to discontinue enrollment of that subgroup.

A Bayesian sequential monitoring design (Thall et al. 1995 and 1998) will be used to monitor the trial for toxicity and futility. Calculations were performed in MultcLean 2.1.

Toxicities will be monitored assuming a prior probability of toxicity following Beta(1,1) against a constant rate of 30% as the maximum acceptable toxicity rate. Trial limiting toxicities (TOX) are any grade 3 or higher toxicities at least possibly related to the study drug that occur in the first 8 weeks of therapy. The trial will be terminated if  $\text{Prob}(\text{TOX} > 0.30 \mid \text{data}) > 0.95$ . Following this rule, the trial will be terminated according to the table below once the first 10 patients have enrolled.

Similarly, efficacy will be monitored assuming a prior probability of response following Beta(0.33,0.67) against a constant rate of 33% as the minimum acceptable response rate. A patient will have a response if there is documented improvement at any time point on the trial. The trial will be terminated if  $\text{Prob}(\text{Response} < 0.33 \mid \text{data}) > 0.975$ . Following this rule, the trial will be terminated according to the following table once the first 10 patients have enrolled.

If there are this many patients treated who are evaluable (i.e., have TOX or completed the first 8 weeks without TOX for TOX, or have at least one IIEF result post-baseline for response)	10	20	30	40

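### Baseline is the only comparator, but the available eligibility text lets in men already taking pentoxifylline or vitamin E, and the analysis does not identify them

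*Combined protocol and SAP*

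**What the plan says.** Section 1.0 gives the type of control as "Comparison to baseline in each patient". Section 11.B counts a man as a responder if his IIEF-5 score rises enough to "move at least 1 category less severe compared to baseline", at any time point. Section 11.C sets the size: "A total of 50 patients will be enrolled".

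The plan treats prior use of the three components differently.

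- **Statin.** Prior use is named in the primary objective (3.0), permitted by inclusion 7 and used to define the three subgroups (1.0, 11.A). It also has its own counting rule in 11.D: "For patients already on statins, this means the patient must have started the combination".
- **Pentoxifylline and vitamin E.** None of the 10 inclusion or 16 exclusion criteria in 4.0 addresses current use. Exclusion 2 concerns contraindication. Exclusion 15 concerns intolerance: "no history of intolerance to pentoxifylline or methylxanthines such as caffeine, theophylline and theobromine".

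The exclusion list does contain current-use rules for other drugs: 5PDE inhibitors, with a 30-day window (item 8), and theophylline (item 13).

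Section 2.0 says of the vitamin E and pentoxifylline pair: "These drugs have been used for radiation induced proctitis as well as cystitis". Section 5.0 A.8 says "current medications including non-prescription substances will be recorded in the medical chart". Section 11.E names prior statin treatment as the planned subgroup factor and otherwise mentions only exploratory work on unspecified baseline features.

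**The concern.** A within-patient comparison measures what changes after baseline. If a man is already taking part of the regimen when he completes the baseline IIEF-5, any benefit from that part is already in his baseline score and cannot appear as a category gain. He still counts fully in the primary proportion and in the futility rule.

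Toxicity could be diluted in a different way. TOX is compared with a fixed 30%, not with baseline. But a man who has stayed on a drug has shown that he tolerates it, and under Section 10.0 a condition present before study therapy is an adverse event only if it worsens.

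Two things are at stake: a response estimate that is too low for men new to the drugs, with somewhat more risk of a futility stop, and a toxicity rule somewhat less likely to stop a regimen that is too toxic for such men.

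**Working it through.** **Inputs from the plan (11.D).** Looks at 10, 20, 30 and 40 men. Stop for toxicity at 6, 10, 14 or 17 or more TOX events. Stop for futility at 0, 2, 5 or 7 or fewer responders. Priors are Beta(1,1) for TOX against 0.30 and Beta(0.33, 0.67) for response against 0.33.

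**Reproducing the plan.** The posterior tail probabilities return exactly these boundaries. An exact binomial recursion over cohorts of 10, with TOX and response independent, gives these values of Pr(stop early):

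| True TOX | True response | Plan | Recomputed |
|---|---|---|---|
| 0.10 | 0.33 | 0.06 | 0.063 |
| 0.30 | 0.33 | 0.17 | 0.172 |
| 0.40 | 0.33 | 0.54 | 0.539 |
| 0.40 | 0.45 | 0.51 | 0.510 |
| 0.50 | 0.45 | 0.89 | 0.892 |

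All 25 tabulated values agree to within 0.01. The design figures contain no error.

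**Adding prior users.** Let q be the share of men already on pentoxifylline or vitamin E. The documents give neither q nor any rate for such men, so everything below is assumed.

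- Pooled response = (1 − q) × 0.33 + q × 0.15. The 33% is the plan's benchmark. The 15% is the lowest response rate in its operating-characteristics table, borrowed as a scenario and not an estimate for these men. TOX is set at 0.10.
- Pooled TOX = (1 − q) × 0.40 + q × 0.10, with response set at 0.45.

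For example, at q = 10% the pooled response is 0.9 × 0.33 + 0.1 × 0.15 = 0.312, and the pooled TOX is 0.9 × 0.40 + 0.1 × 0.10 = 0.37.

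| q | Pooled response | Pr(stop early), response scenario | Pooled TOX | Pr(stop early), TOX scenario |
|---|---|---|---|---|
| 0 | 0.330 | 0.063 | 0.400 | 0.51 |
| 2% (one man in 50) | 0.326 | 0.068 | 0.394 | 0.48 |
| 5% | 0.321 | 0.076 | 0.385 | 0.44 |
| 10% | 0.312 | 0.091 | 0.370 | 0.37 |
| 20% | 0.294 | 0.129 | 0.340 | 0.24 |

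**Allowing for the first look.** Section 11.A says 11 men were enrolled at the 2021 revision and that the first interim analyses allow continuation. The probability of stopping later, given that look 1 was passed, is (total − look 1) / (1 − look 1). In the response scenario:

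- q = 0: (0.0630 − 0.0184) / (1 − 0.0184) = 0.045
- q = 10%: (0.0911 − 0.0239) / (1 − 0.0239) = 0.069

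**The case against.** The strongest reply is that nothing shows prior use to be common. Section 2.0 says the pair has been used for radiation proctitis and cystitis, which makes prior use plausible in men who have had prostate radiation, but it gives no frequency. With one prior user in 50, both scenarios barely move. This stands: the size is unknown and could be negligible.

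Several stronger inferences are tempting, and the documents do not support them.

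- *Prior users compare the full regimen with itself.* That needs a man on a statin and both other drugs at the study doses. A man on a vitamin E supplement alone still adds pentoxifylline, and may also add a statin or a higher vitamin E dose. For most partial users the dilution would be partial.
- *Their follow-up clock began before enrolment.* Table 1 says "follow up times start from the day patient begins taking all 3 drugs concurrently". But Section 6.0 allows no protocol therapy before full enrolment, so the natural reading is the protocol regimen, started afterwards.
- *The plan has no rule at all for these drugs.* The prescribing figure in 7.0 is not shown, and its legend mentions the vitamin E and pentoxifylline combination. The appendices are also missing. The statement can cover only the text available.
- *The design requires a baseline free of study drugs.* The plan openly accepts prior statin use, so that is not its stated requirement.

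Two further replies have partial force. Exclusion 11, on drugs with anti-platelet properties, is open-ended, and an investigator might apply it here; but it names neither drug, so its effect would depend on the reader. The chart history in 5.0 A.8 and the exploratory analyses in 11.E would allow prior users to be found, but nothing commits the trial to doing so. Finally, dilution of response works against the regimen and cannot create a false positive; this does not answer the toxicity side.

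**Conclusion.** The gap holds in a limited form. The available eligibility text admits men already on pentoxifylline or vitamin E, and the analysis does not separate them, although each man's baseline is the only comparator. The response proportion is biased downward if prior users gain a category less often than new users. The TOX rate is diluted if they have fewer qualifying events; that is likely but not certain.

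Under the stated assumptions, a share of 2% to 10% raises Pr(stop early) from 0.063 to between 0.068 and 0.091. Given that the first look has been passed, the rise at 10% is from 0.045 to 0.069. On the toxicity side, the chance of stopping at a true rate of 0.40 in new users falls from 0.51 to between 0.48 and 0.37. The 20% row shows the trend and is not a forecast. All of this depends on an unknown share, on how complete the prior use is, and on borrowed rates for prior users.

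A reader might infer that the stopping boundaries or the sample size are wrong. They are not: they reproduce, and the fix does not alter them. This is a cheap improvement to interpretability.

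**What to change.** 1. For men still to be enrolled, add a criterion to 4.0 that the baseline IIEF-5 is completed while not taking pentoxifylline or a vitamin E supplement. Any interval, and any handling of existing treatment, is for the sponsor to decide.
2. For all men, including those already enrolled, move prior use and dose of both drugs from the 5.0 A.8 chart history into the study database. In 11.E, report the any-time response proportion and the TOX rate for all treated men, and again without prior users.
3. Leave the stopping-rule counts in 11.D on all treated men. That section counts anyone who received at least one dose, and removing treated men from a safety count would conflict with it.

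The cost is one criterion, the database entry and one tabulation, plus the possible loss of a few otherwise eligible men from a trial that accrues slowly.

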## 2.0 Background & Rationale

Prostate Cancer is the most common cancer diagnosed among men in the US, accounting for roughly 33% of all non-skin cancer diagnoses each year. Standard first line

therapy for localized prostate cancer include surgery, external beam radiotherapy, and interstitial brachytherapy. The most common side effect of radiation therapy in any form is erectile dysfunction (ED). Depending on radiation technique and associated risk factors, the documented incidence of ED varies. However, reports indicate that anywhere from 10% to 84% of all patients who undergo radiation therapy (XRT) will develop some degree of ED after treatment. Rates vary widely due to heterogeneity of treatment techniques as well as patient populations and risk factors including age, race, comorbidities, etc. Difficulties in assessing ED arise with patient reported outcomes as well, as in one study only 43% of patients who verbally reported being fully potent were found to have normal IIEF scores. However, objective analysis with the IIEF now makes assessment less inherently biased and easier to analyze. Regardless of exact incidence, post-XRT erectile dysfunction plays a significant role in patients' quality of life.

The molecular and cellular events leading to late toxicity after RT begin virtually immediately after the first exposure to ionizing radiation. Endothelial cell damage plays an important role in this process, and recent evidence suggests that the capillary endothelial cell may be the first cellular element to be damaged by RT. Vascular damage is important in the phenotype of RT-induced rectal injury, where telangiectatic vessels are often responsible for the bleeding characteristic of this condition. The cholesterol lowering agents HMG coA reductase inhibitors (statins) have been demonstrated to reduce the risk of myocardial infarction, in part, through their vascular protective effects, which are not dependent on changes in serum cholesterol levels. In vitro, statins have been shown to protect human endothelial cells from ionizing radiation. Multiple mechanisms appear to be involved, including attenuation of extracellular stress responses, down-regulation of chemokines and chemokine receptors, and by exerting anti-inflammatory and anti-thrombotic effects on these cells. In vivo,

lovastatin has been shown to protect mice from the effects of whole lung irradiation for up to 24 weeks . Mice receiving lovastatin demonstrated improved survival, a decreased inflammatory response in the lung and reduced fibrosis. Thus, statins may have the potential to protect against RT-induced late effects.

The exact mechanism of radiation induced erectile dysfunction is poorly understood currently. We know the veno-occlusive mechanism of achieving and maintaining a functional erection involves multiple processes which may be affected by radiation. One study in particular suggested a vasculogenic mechanism as the predominant factor contributing to radiation induced erectile dysfunction . Another noted morphologic changes and resulting loss of tone in the internal pudendal artery after SBRT (stereotactic body radiation therapy) in canines . Along with vascular damage playing a major role, chronic oxidative stress has recently been investigated in ED, as it is a known contributor to radiation induced normal-tissue injury in other situations. A recent study using single fraction radiotherapy in a rat model of RT induced ED investigated the role of chronic oxidative stress in development of post-radiation ED using an image guided radiation technique which mimics what is used in clinics currently . Pathophysiologic evidence pointed to early events which may be inflammatory in nature with a resultant decrease in eNOS (endothelial nitric oxide synthase) and subsequent NO (nitric oxide) production. This may be the cause of noted damage to the Cavernosal Nerve and subsequent decreases in intracavernosal pressure, decrease in smooth muscle content, increase in collagen deposition and decreased perfusion in the corpora cavernosa.

For treatment of post-RT erectile dysfunction, 5-PDE inhibitors are typically the first line therapy (i.e. Sildenafil). However, although these drugs are effective, the cost is prohibitive for

most patients, and these agents are rarely covered by patients' health insurance. This explains the need for less-expensive, yet effective treatment options.

Statins have been studied for a role in the treatment of established ED, although, until recently, not in the setting of radiation induced ED. A recent meta-analysis of all trials investigating the efficacy of Statin use on non-radiation induced ED showed a clinically and statistically significant increase of 3.4 points on the IIEF. Of note, this was roughly 1/3 to ½ of the effect seen with PDE inhibitors. The most commonly used statins were atorvastatin followed by simvastatin. Statins improve endothelial function both by lowering LDL (low density lipoprotein) levels and by increasing the availability of NO. Thus, statins appear to counteract one of the primary molecular processes implicated in the development of radiation induced ED. A recent secondary analysis of a trial studying the ability of lovastatin to prevent radiation induced rectal injury demonstrated that this agent was effective in preserving erectile function across most domains of the IIEF with a minimum of 2 years follow-up. More potent statins, such as atorvastatin, might prove even more effective in this setting.

As noted above, along with decrease in NO production resulting from the inflammatory response to RT, fibrosis also appears to be a component of radiation induced ED. As such, the combination of Vitamin E and Pentoxifylline may provide a benefit as this combination has a proven role in the treatment of established soft tissue fibrosis from radiation. These drugs have been used for radiation induced proctitis as well as cystitis. Additionally, a recent study has shown that prophylactic Vit E and Pentoxifylline reduces the rate of post-mastectomy fibrosis and implant loss in women with breast cancer. Thus, the addition of Vitamin E plus Pentoxifylline to atorvastatin, as proposed in this study, will target both the proinflammatory and profibrotic pathways known to play a role in late radiation injury.

Another rationale for the combination of these agents is their well-established favorable side effect profile. All of these agents have been used for many years in the clinic and are generally well-tolerated. In addition, are all off-patent and are less costly than the 5-PDE inhibitors.

